5.2.7. Progression-free Survival

Since disease progression is assessed periodically, PD can occur any time in the time interval between the last assessment where PD was not documented and the assessment when PD is documented.

Hence, progression-free survival (PFS) is defined as the time (months) from date of first dose date of study drug for patients in Part 1 or date of randomization for patients in Part 2 until date of documented disease progression or death due to any cause, whichever comes first. More specifically, PFS will be determined using all the assessment data up until the last evaluable visit prior to or on the date of (i) disease progression as defined by RECIST 1.1 (Eisenhauer et al,

2009) or by clinical criteria (this will not apply to the BICR analysis); or (ii) withdrawal of consent; or (iii) receiving subsequent anti-cancer therapy, whichever is earlier.

PFS will be calculated using two response data sets: derived and BICR. For PFS determined by BICR, only progression per RECIST will be considered. For PFS as determined by derived, either clinical progression or progression by RECIST (whichever comes first) will be considered.

Death, regardless of cause, is always considered as a PD event. The detailed censoring rules for the analysis are summarized in [Table 18](#).

Table 18 Assignment of Progression or Censoring Based on Radiological Assessment

Situation	Date of Progression or Censoring	Outcome
No Baseline assessment	Date of first dose of study drug for patients in Part 1 or date of randomization for patients in Part 2	Censored
No progression	Date of last adequate radiological disease assessment	Censored
Treatment discontinuation for reasons other than disease progression	Date of last progression assessment with no documented progression	Censored
New anticancer treatment started prior to documented disease progression	Date of last adequate radiologic assessment no later than the initiation of new anticancer treatment	Censored
Disease progression	Date of the first reported progression	Progressed
Death without a PD	Date of death	Progressed
Investigator claim of clinical progression	Date of the investigator assigned PD	Progressed

Note: An adequate radiologic assessment is defined as an assessment where the Investigator determined radiological response is CR, PR, SD, or PD. If PD and new anti-cancer therapy occur on the same day, will assume that the progression was documented first, e.g. outcome is progression and the date is the date of the assessment of progression.

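### SAP Table 18 censors patients who stop treatment without progression, which contradicts the PFS definition in the same section; no rule says which prevails, and duration of response inherits the conflict

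*SAP*

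**What the plan says.** SAP 5.2.7 defines PFS from first dose (Part 1) or randomization (Part 2) "until date of documented disease progression or death due to any cause, whichever comes first". It then sets the data window: "PFS will be determined using all the assessment data up until the last evaluable visit prior to or on the date of" the earliest of three events. The first is progression; the other two read "ii) withdrawal of consent; or (iii) receiving subsequent anti-cancer therapy, whichever is earlier". Stopping study treatment is not among them. The section adds that a death from any cause is always an event.

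The same section continues "The detailed censoring rules for the analysis are summarized in" Table 18. Three rows matter here:

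- The disease-progression row has the outcome progressed, and its date is given as "Date of the first reported progression".
- The row at issue, "Treatment discontinuation for reasons other than disease progression", has the outcome censored. Its date column reads "Date of last progression assessment with no documented progression".
- The row for patients without progression also has the outcome censored, but with a differently worded date: "Date of last adequate radiological disease assessment".

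Duration of response (SAP 5.2.6.4) has its own sentence, which censors only patients without progression or death. It then refers to 5.2.7 for its censoring rules.

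**The concern.** Stopping treatment without progression is the ordinary end of chemotherapy in this trial. Protocol 6.1.3 and SAP 2.2 give completion of six cycles as an example of investigator discontinuation, and SAP 6.2.1 tabulates patients who discontinue after six cycles. Protocol 6.1.5 and 10.7 and SAP 5.2.6 keep scanning patients who stop without progression about every two months. The trial therefore deliberately collects progressions that occur after treatment has stopped, and Table 18 leaves their status open.

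PFS is a secondary endpoint, but SAP 6.2.8.8 gives it a between-arm Cox p-value and a hazard ratio with 95% CI, on both the central-review and the derived data. Two programmers working from 5.2.7 could produce different event counts, hazard ratios and durations of response from the same data. If the row is applied literally, progressions seen on scheduled post-chemotherapy scans drop out of the comparison.

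**Working it through.** **Comparing the rules.** Take a patient who completes six cycles without progression, starts no new therapy, stays in follow-up, and progresses on a two-monthly scan.

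- Definition in 5.2.7: event, at the documented progression.
- Data window in 5.2.7: the scan counts, because none of the three cut-offs came earlier.
- Disease-progression row: progressed. The row is not limited to progression on treatment.
- Discontinuation row: censored. The row is not limited to patients who never progress.

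Nothing settles this pair. The new-treatment row carries its own ordering, since it applies only before documented progression. The note under Table 18 settles only progression and new therapy on the same day. The sentence on deaths arguably settles a death after discontinuation, but no such sentence covers progression on a scan. The row's date is also not tied to the date of stopping.

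Protocol 13.5.2 likewise censors only patients without progression or death. It also allows the SAP to add censoring techniques for PFS, so no conflict with the protocol is claimed.

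**Size if the row is applied literally.** The documents give no figure to reproduce and no median PFS, so this is an illustration. Inputs:

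- From the documents: 70 patients in Part 2; 21-day cycles, so six cycles = 126 days; scans after every even cycle (days 42, 84, 126), then every 60 days; 11 months of accrual, 4.5 months of treatment and 1 month of safety follow-up (Protocol 6.1.3).
- Derived: follow-up at the final analysis (SAP 6.2.12) runs from 4.5 + 1 = 5.5 months to 5.5 + 11 = 16.5 months, taken as uniform.
- Assumed: exponential PFS with median 4 to 7 months; every patient without progression stops at day 126; deaths without progression form 0, 10 or 20% of PFS events; median survival after progression 3 or 6 months; progression documented at the next scan.

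Share of PFS events after day 126 = exp(−ln 2 × (126/30.4375)/median). For a 4-month median this is exp(−0.693 × 4.14/4) = 0.488.

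Simulated mean event counts at the final analysis (2,000 trials of 70 patients per scenario), where the literal row still counts deaths without documented progression:

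| Assumed median (months) | Share after day 126 | Events, no row | Events, literal row |
|---|---|---|---|
| 4 | 0.488 | 55.7–56.5 | 38.1–43.9 |
| 5 | 0.563 | 50.8–51.4 | 32.9–38.5 |
| 6 | 0.620 | 46.6–47.2 | 29.0–34.7 |
| 7 | 0.664 | 42.8–43.5 | 25.9–31.3 |

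Between 12.2 and 17.8 patients fit both rows. With SE(log HR) = 2/√events, the SE without the row runs from 2/√56.5 = 0.27 to 2/√42.8 = 0.31. With the literal row it runs from 2/√43.9 = 0.30 to 2/√25.9 = 0.39.

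**Sensitivity.**

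- If 30% of patients event-free at day 126 start new therapy within 120 days and are censored there in both versions, the counts are 38.3–52.0 without the row and 25.3–42.3 with it; 9.4–13.8 patients fit both rows.
- With an assumed 24-month follow-up: 63.3–68.9 against 27.9–47.9. Adding the 30% new-therapy assumption: 52.8–60.8 against 26.8–45.2.
- Check by hand: with 12 months of follow-up for everyone, exact event times and all events after day 126 dropped, a 6-month median gives 70 × (1 − exp(−ln 2 × 12/6)) = 52.5 events without the row and 70 × (1 − 0.620) = 26.6 with it.

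**The case against.** The strongest reply is that the harmless reading is probably the intended one. The definition, the data window, the sentence on deaths, the duration-of-response sentence and Protocol 13.5.2 all tie censoring to event-free patients. The row's date is the last clean assessment rather than the date of stopping. Applied to a patient who later progresses, it would use clean follow-up scans and discard only the one showing progression, which is an odd rule to intend. Rows in this table overlap elsewhere too, so redundancy alone proves nothing. PFS is listed among the safety endpoints of a study the protocol calls descriptive, and SAP 6.1.1 requires independent validation of the programs.

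Much of this stands as evidence of intent, and it is why the point is a contradiction to resolve and not a finding that events will be lost. It is also fair that the body text limits all PFS assessments to the period before new therapy, whichever row applies; what the row lacks is any bound linked to discontinuation. The event counts do rest on assumptions. Six cycles is only an example in the protocol, cycles may be delayed, and if prophylactic cranial irradiation is treated as new anti-cancer therapy, more responders would be censored under either version.

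The reply does not remove the contradiction. The SAP nowhere states the harmless reading, which would make the row repeat the no-progression row. A separate row with differently worded dates invites separate handling. Validation against the SAP cannot settle a case on which the SAP gives two answers.

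**Conclusion.** The concern holds. Within SAP 5.2.7, the definition and the disease-progression row count a progression found after treatment has stopped, while the discontinuation row censors the same patient, with no stated precedence between them. Duration of response inherits this. Because completing chemotherapy is itself a discontinuation without progression, the case is routine.

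Under the harmless reading the numerical effect is zero. Under the literal reading, the illustration gives about 26 to 44 PFS events against 43 to 56 at the final analysis, and a wider gap with longer follow-up. Those sizes depend on the assumed median PFS, follow-up, stopping time and new-therapy rate; the contradiction does not. It should be fixed, since the affected endpoint carries a between-arm hazard ratio and p-value.

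**What to change.** Settle this before unblinding, which SAP 6.2.12 places at the final analysis, so that the choice cannot depend on results.

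- Delete the discontinuation row from Table 18, or limit it to patients with no later documented progression or death.
- State in 5.2.7 that the first documented progression or death counts whether or not treatment has stopped, subject to the existing consent-withdrawal and new-therapy rules.
- State which row prevails when a patient fits more than one.
- Apply the same rules to duration of response in 5.2.6.4.
- If a version that censors at discontinuation is wanted, label it a sensitivity analysis and give it an explicit date bound.

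This costs one or two lines of SAP text and the matching programming. The follow-up scans are already scheduled, so no new data are needed.

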5.2.8. Overall Survival

Overall survival is calculated as the time (months) from date of first dose of study drug for patients in Part 1 or date of randomization for patients in Part 2 to the date of death due to any cause. Patients who do not die during the study will be censored at the date last known to be alive. Patients lacking data beyond the day of first dose of study drug for patients in Part 1 or date of randomization for patients in Part 2 will have their survival time censored at day of first dose of study drug for patients in Part 1 or date of randomization for patients in Part 2. OS will not be censored if a patient receives other anti-tumor treatments after the study drugs.

6. ANALYSIS METHODS

6.1. General Principles of Analysis

6.1.1. General Methodology

In general, all efficacy, safety and PK variables will be summarised using descriptive statistics and graphs as appropriate. Continuous variables will be summarised by descriptive statistics (sample size (n), mean, standard deviation (SD), minimum, median, and maximum). Categorical variables will be summarised in frequency tables (frequencies and percentages). For PK variables, the geometric mean and coefficient of variation (CV) will be used instead of the arithmetic mean and SD, if appropriate. Time to event variables will be analysed with Kaplan-Meier method and summarized with median, twenty-fifth and seventy-fifth percentiles, and 95% confidence intervals (CI), if applicable. Individual data will be presented in patient listings.

Analyses will be implemented using SAS[®] 9.1 or higher (SAS Institute, Cary, North Carolina, USA). The International Conference on Harmonisation (ICH) numbering convention, i.e. ICH-E3, will be used for all tables and listings. Upon completion, all SAS[®] programs will be validated by an independent programmer within the staff of the third-party vendor doing the primary analysis. In addition, the programming needed to generate a subset of outputs will be validated by an independent validation vendor. The validation process will be used to confirm that statistically valid methods have been implemented and that all data manipulations and calculations are accurate. Checks will be made to ensure accuracy, consistency with this plan, consistency within tables, and consistency between tables and corresponding data listings.

All summary tables, listings, and figures (TLFs) will be presented by treatment groups as defined in [Table 19](#).

Table 19 Treatment Display in TLFs

Study Part	G1T28 Dose	Treatment Description in Data Display
Part 1	200 mg/m ²	G1T28 200 mg/m ²
Part 1	240 mg/m ²	G1T28 240 mg/m ²
Part 1		G1T28 Total [a]
Part 2	240 mg/m ²	G1T28 240 mg/m ²
Part 2	Placebo	Placebo
Parts 1 and 2	240 mg/m ²	G1T28 240 mg/m ² [b]

[a] Summarize all G1T28 dose groups in Part 1.

[b] Summarize all G1T28 dose group 240 mg/m² in Part 1 and Part 2, it will be included in the summary for safety data.

All statistical tests will be conducted at a two-sided significance level of 20% unless otherwise specified. For Part 2 data, the G1T28 + E/P therapy will be compared to the placebo + E/P therapy group. Where appropriate, model-based point estimates, together with their 80% CIs will be presented along with the two-sided p-values for the tests. P-value will be presented to 4 decimal places, if the p-value <0.0001, the value will be presented as “<0.0001”.

For continuous data, the same number of decimal places as in the raw data will be presented when reporting mean, median, minimum and maximum; one more decimal place than in the raw data will be presented when reporting SD and standard error (SE). The derived variables will be presented with 1 decimal place. Percentages will be reported with 1 decimal point; if the count is

0, no percentage will be presented. Value of percentage less than 1% will be presented as “<1%.” Value of percentage less than 100% but $\geq 99.5\%$ will be presented as “>99%.”

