Immunologic Marker Assessment	In Part 2 of the study, peripheral blood samples will be collected at predose on Day 1 of Cycles 1, 3, and 5; at the Post-Treatment Visit; and at 60 days after the Post-Treatment Visit.
Statistical Analysis	
Data will be summarized separately by study part (Part 1 and Part 2). Data from Part 1 will be summarized descriptively by dose level, if applicable, and overall. Data from Part 2 will be summarized descriptively by treatment group and overall. Treatment differences between treatment groups for Part 2 will be calculated as G1T28 + E/P therapy minus Placebo + E/P therapy. Select safety summaries will include combined data from both Parts 1 and 2 of the study. The descriptive summary for the categorical variables will include counts and percentages. The descriptive summary for the continuous variables will include means, medians, standard deviations, and minimum and maximum values. The descriptive summaries of time to event data will include median, twenty-fifth and seventy-fifth percentiles, and standard error. All data will be listed for all patients. This study is descriptive in nature, and no formal hypothesis testing will be performed across treatment groups. All confidence intervals (CIs) will be 95%, unless stated otherwise.
 
A DMC will review accumulating safety and disposition data during the Treatment Phase for patients randomized in Part 2. The final analysis will be performed after all patients have completed the Post-Treatment Visit. A supplemental analysis including the cumulative data collected during the Survival Follow-up Phase will be completed at the end of study.
 
The full analysis set (FAS) includes all patients who received at least 1 dose of study drug and will be the primary population for efficacy and exploratory endpoints. Full analysis set analyses will be conducted on the basis of the assigned treatment. The safety population includes all patients who received at least 1 dose of study drug and will be the population used for the analysis of safety endpoints. The safety population will be conducted on the basis of the actual treatment received. A per-protocol (PP) subset may also be used to analyze select endpoints and will be based on study drug exposure (compliance and/or time on study drug) and major protocol deviations. The PK analysis set will include all dosed patients in the Phase 1b dose-finding portion of Part 1 with evaluable PK data.
 
Summaries of efficacy will be performed using the FAS on hematologic kinetics, hematologic toxicity, infections, growth factor and antibiotic use, transfusions, chemotherapy exposure, and patient-reported QOL scores. Select summaries will also be repeated in the PP analysis set. Unless noted otherwise, hematologic endpoints will be summarized separately by each parameter type (ie, ANC,

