### 13.2.3. General Considerations for Data Analysis

All statistical analyses will be performed using SAS® version 9 or higher.

Data will be summarized separately by study part (Part 1 and Part 2). Data from Part 1 will be summarized descriptively by dose level if applicable and overall. Data from Part 2 will be summarized descriptively by treatment group and overall. Treatment differences between treatment groups for Part 2 will be calculated as G1T28 + E/P therapy minus placebo + E/P therapy. Select safety summaries will include combined data from both Part 1 and Part 2 of the study. The descriptive summary for the categorical variables will include counts and percentages. The descriptive summary for the continuous variables will include means, medians, standard deviations, and minimum and maximum values. The descriptive summaries of time to event data will include median, twenty-fifth and seventy-fifth percentiles and standard error. All data will be listed for all patients. Unless specified otherwise, safety summaries will include all collected data, and summaries of efficacy will include data collected through the Treatment Phase.

This study is descriptive in nature, and no formal hypothesis testing will be performed across treatment groups. All CIs will be 95%, unless stated otherwise.

The effects of covariates and withdrawal from study treatment due to reasons other than death, disease progression, and toxicity will be assessed to determine the impact on the general applicability of results from this study. Further details of the analysis, including the handling of missing data, impact of variable chemotherapy dose exposure including dose reductions, transformations and other data handling procedures will be provided in a separate SAP. Exploratory analyses of the data will be conducted as deemed appropriate.

Summaries that are based on within-cycle, including changes, events, or findings, will require a clear definition of “end of cycle” that accounts for variable durations in the cycle due to within-cycle dosing delays, delays in subsequent cycle initiation, and incomplete cycles. This will be discussed in the SAP for each applicable endpoint.

Protocol violations will be fully defined and documented before unblinding.

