6.2.7. Efficacy Analyses

All the efficacy variables will be summarized using descriptive statistics by cycle or visit, with the supportive data provided in patient listings. Part 1 will be summarized using only descriptive statistics. For Part 2, in addition to the descriptive summary, the between treatment comparison (trilaciclib vs placebo), if applicable, will be performed only for those prospectively-defined endpoints outlined in [Section 5.1.1](#). For these comparisons, all statistical tests will be conducted at a two-sided significance level of 20% unless otherwise specified. Where appropriate, model-based point estimates, together with their two-sided 80% CIs will be presented along with the two-sided p-value for the test. Graphical presentation of efficacy results will be appropriately performed as needed.

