6.2.7.1. Prospectively-Defined Efficacy Analyses

Detailed information for the prospectively-defined efficacy endpoints can be found in [Section 5.1.1](#). A binary response variable (Yes, No) will be analyzed to compare G1T28 and placebo using stratum-adjusted method to account for the ECOG status (0-1 vs 2) as the stratification factor. The adjusted proportion difference (trilaciclib vs placebo) and its 80% CIs will be calculated using CMH weight outlined in [Kim et al. 2013](#). The two-sided p-value will be calculated using stratified exact Cochran-Mantel-Haenszel (CMH) method. The following binary response variables will be analyzed:

- Occurrence of a febrile neutropenia AE during the treatment period (refer to [Section 5.1.1.1](#));
- Occurrence of a RBC transfusion (actual and eligible) during the treatment period (refer to [Section 5.1.1.2](#));
- Occurrence of a platelet transfusion (actual and eligible) during the treatment period (refer to [Section 5.1.1.3](#));
- Occurrence of a GCSF administration during the treatment period (refer to [Section 5.1.1.4](#));

- Occurrence of an ESA administration during the treatment period (refer to [Section 5.1.1.5](#));
- Occurrence of an IV antibiotic administration during the treatment period (refer to [Section 5.1.1.6](#));
- Occurrence of an infection SAE during the treatment period (refer to [Section 5.1.1.7](#));
- Occurrence of a pulmonary infection SAE during the treatment period (refer to [Section 5.1.1.7](#)).

Time (days) to event endpoints will be summarized using Kaplan-Meier method, and the descriptive statistics of median, 25% and 75% percentiles along with their 95% CIs will be calculated for endpoints described in [Sections 5.1.1.8, 5.1.1.9, and 5.1.1.11](#).

In addition to the summary from Kaplan-Meier method, for the endpoints of

- Overall duration (days) of Grade 4 neutropenia;
- Overall duration (days) of Grade 3/4 neutropenia;
- Time (days) to first occurrence of a MAHE event,

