the two-sided p-value will be obtained from the stratified Kaplan-Meier method to account for the ECOG status (0-1 vs 2) as the stratification factor. The hazard ratio (HR) between the two treatments (trilaciclib vs placebo), together with its 80% CIs will be calculated from a Cox proportional hazard model in which treatment and baseline ECOG status (0-1 vs 2) will be included as fixed effects. For the time (days) to first occurrence of a MAHE event, a graphical display of cumulative incidence will be presented.

For the endpoints specified in [Section 5.1.1.10](#), in addition to descriptive statistics summary, appropriate graphical display will be provided to help viewing the trend of change over time. Moreover, each of the ANC change over time (i.e. observed value at windowed visit, cycle NADIR, and ANC at each scheduled Day 1 of a cycle) specified above will be done using three distinct data sets to evaluate the confounding effect of GCSF administration: all patients or cycles regardless of GCSF administration; inclusion of only those patients or cycles who had concurrent GCSF administration; and inclusion of only those patients or cycles who did NOT have concurrent GCSF administration. The “with” and “without” GCSF analyses are subsets of the total patient or cycles.

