6.2.8.8. Analyses of PFS and OS

The analysis method as described in [Section 6.2.7.1](#) for time to event data will be applied to the following variables

- PFS (BICR and derived)
- OS

The analyses are based on the FAS. The supportive data listings will also be provided.

For the PFS from both BICR and derived responses and OS, a comparison will be conducted between G1T28 and placebo in Part 2. The two-sided p-value from a Cox proportional hazard model will be presented, the model includes treatment and baseline ECOG status (0-1 vs 2) as fixed effects. The hazard ratio (HR) between the two treatment groups, together with its 95% CIs will be presented.

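### Twelve Part 2 between-arm comparisons in the SAP use a two-sided 20% level and 80% CIs; the protocol plans 95% CIs and no formal testing, and SAP Section 7 does not declare the change

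*SAP*

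**What the plan says.** **Protocol.** Section 13.2.3 states: "This study is descriptive in nature, and no formal hypothesis testing will be performed across treatment groups". It continues: "All CIs will be 95%, unless stated otherwise". The Statistical Analysis part of the synopsis repeats both. For Part 2 rate differences, 13.4.2.2 plans two-sided 95% intervals. Section 13.4.2.4 has infections, red cell and platelet transfusions, systemic antibiotic use and hematopoietic growth factor use reported in the same way. The protocol is not entirely free of tests: 13.4.2.1 tests treatment-by-covariate interactions, and 13.4.2.2 allows an optional recurrent-events model with a test between groups.

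**SAP.** The 20% level is set in 6.1.1: "All statistical tests will be conducted at a two-sided significance level of 20% unless otherwise specified". It is repeated for the prospectively defined comparisons in 6.2.7: "all statistical tests will be conducted at a two-sided significance level of 20% unless otherwise specified". Both sections pair it with 80% intervals and two-sided p-values. For the eight binary endpoints, 6.2.7.1 says: "The adjusted proportion difference (trilaciclib vs placebo) and its 80% CIs will be calculated using CMH weight". Section 6.2.8.7 uses the same method for ORR. For the two neutropenia durations and time to first major adverse hematologic event (MAHE), the hazard ratio is given "together with its 80% CIs will be calculated from a Cox proportional hazard model". For PFS and OS, 6.2.8.8 gives the hazard ratio a 95% interval and adds: "The two-sided p-value from a Cox proportional hazard model will be presented". It names no test level.

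**Declared changes.** By its own introduction, SAP Section 7 is a list of endpoints and analyses that were removed. The recurrent-events model is on it. The added between-arm tests, the 20% level and the 80% intervals are not.

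**The concern.** A reader of the protocol expects estimates with 95% intervals and no verdict on significance. A reader of the SAP's tables will see 80% intervals and p-values judged at 20%. Some intervals will exclude no difference where the interval the protocol planned would include it, and p<0.20 could be taken as a positive result in a study described as descriptive. No multiplicity adjustment is stated. Because the section headed as changes from the protocol is silent, nothing alerts the reader that the standard has moved, and the SAP gives no reason for choosing 20%.

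**Working it through.** **1. Count the comparisons.** SAP 6.2.7.1 lists eight binary endpoints: febrile neutropenia, red cell transfusion, platelet transfusion, G-CSF, ESA, IV antibiotics, infection SAE and pulmonary infection SAE. It adds three hazard ratios: duration of Grade 4 neutropenia, duration of Grade 3/4 neutropenia and time to first MAHE. SAP 6.2.8.7 adds ORR. That is 8 + 3 + 1 = 12 at 80%. PFS (central review and derived) and OS make 3 at 95%, so 12 of 15 are at the lower level.

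**2. Sort them by what the protocol says.**

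| Comparison | Protocol basis for 95% |
|---|---|
| Red cell and platelet transfusion, G-CSF, ESA, IV antibiotics, infection SAE, pulmonary infection SAE (7) | Categories named in 13.4.2.4, which refers back to the hematologic incidence reporting; 13.4.2.2 gives two-sided 95% for the difference |
| Febrile neutropenia, three hazard ratios, ORR (5) | Only the default in 13.2.3 |

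**3. Reproduce the plan's own figure.** Protocol 13.1 and SAP 2.3 give ±0.157 per arm (95% Wilson, n = 35). The half-width is z/(1 + z²/n) × √[p(1−p)/n + z²/(4n²)]. With z = 1.960 and p = 0.5 this is 0.1572, which agrees. It describes one arm, not a difference, so it is a check on the inputs only.

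**4. Relative width.** z(0.90) = 1.2816 and z(0.975) = 1.9600. The ratio is 1.2816/1.9600 = 0.654; the inverse is 1.529.

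**5. Difference in proportions, 35 per arm** (unstratified Wald, half-width z√[2p(1−p)/35]):

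| Common rate | 80% | 95% |
|---|---|---|
| 0.5 | ±0.153 | ±0.234 |
| 0.2 | ±0.123 | ±0.187 |

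**6. Worked example, 14/35 against 21/35.** The difference is 0.40 − 0.60 = −0.20. The standard error is √[(0.24 + 0.24)/35] = 0.1171.
- 80%: −0.20 ± 1.2816 × 0.1171 = −0.35 to −0.05.
- 95%: −0.20 ± 1.9600 × 0.1171 = −0.43 to +0.03.

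Newcombe score intervals tell the same story: −0.340 to −0.047 at 80% and −0.404 to +0.032 at 95%.

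**7. Interval against planned test.** The SAP takes its binary p-values from a stratified exact CMH test, so a Wald interval that excludes zero is not the same as p<0.20. Unstratified Fisher p-values give a guide:

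| Patients with event, of 35 | Wald 80% CI | Wald 95% CI | Fisher p |
|---|---|---|---|
| 14 v 21 | −0.350 to −0.050 | −0.430 to +0.030 | 0.15 |
| 15 v 21 | −0.322 to −0.021 | −0.402 to +0.059 | 0.23 |
| 4 v 10 | −0.291 to −0.052 | −0.354 to +0.012 | 0.13 |
| 5 v 10 | −0.267 to −0.019 | −0.332 to +0.046 | 0.24 |

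All four 80% intervals exclude zero and none of the 95% intervals does, but only two of the four pairs reach p<0.20 by the Fisher test.

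**8. Hazard ratios.** The limits are the estimate multiplied and divided by exp(2z/√d). The documents give no event count for the neutropenia durations or MAHE, so d = 40 to 70 is an assumption.

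| Events | 80% factor | 95% factor |
|---|---|---|
| 40 | 1.50 | 1.86 |
| 70 | 1.36 | 1.60 |

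**The case against.** The best defence is that protocol Section 13 leaves full statistical detail to the SAP, and its 95% rule yields where something else is stated. For febrile neutropenia, the three hazard ratios and ORR that argument has force: the SAP does state otherwise, and these five depart from a default only. It has less for the other seven, where the protocol gives 95% for the category. Even there the SAP endpoints are narrower or redefined (IV antibiotics only, serious infections from a fixed term list, transfusion counted when a laboratory value makes the patient eligible), so the protocol fixed the level for the category rather than for the exact endpoint. The clause also qualifies intervals only; it does not reach the sentence that excludes formal testing.

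It is also fair to say that the comparisons are not hidden. SAP Section 4 lists the endpoints, 6.2.7 and 6.2.7.1 give the tests and levels, and Section 1 says decisions precede database lock. The defect is an undeclared and unexplained departure, not a concealed one. A relaxed level can be reasonable in a small phase 2 study, but the SAP does not make that case.

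Three stronger readings are tempting and not supported:
- **That SAP 2.3 contradicts the 80% intervals because its precision is at 95%.** That statement is per arm, and the SAP's explicit within-arm intervals (Kaplan-Meier percentiles, Clopper-Pearson response rates) are also at 95%.
- **That PFS and OS are plainly tested at 20%.** The general default could apply, but pairing those p-values with 95% intervals could equally be read as specifying otherwise. The level is unclear.
- **That the protocol forbids every test.** It has the interaction tests and the optional recurrent-events test, though neither supports a 20% level across twelve comparisons.

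**Conclusion.** The point holds as a reporting inconsistency that should be fixed. Twelve of fifteen Part 2 comparisons are set at 80% and 20%. The conflict with the protocol is direct for seven of them and is with the default for five, and Section 7 is silent on all of them. The intervals would be about a third narrower than the protocol plans, enough to change the reading of a 20-point difference between arms of 35.

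The widths ignore ECOG stratification and use Wald approximations; the hazard ratio factors rest on assumed event counts. The ratio of 0.654 depends on neither, as it needs only normal-based limits. A reader might infer that the trial's size or a go/no-go decision was built on the 20% level. The documents do not support that: both say the sample size rests on clinical rather than statistical considerations, and neither gives a power calculation or success rule. The consequence is confined to interpretation and reporting.

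**What to change.** 1. Report 95% intervals for the seven Part 2 differences covered by protocol 13.4.2.2 and 13.4.2.4. For febrile neutropenia, the three hazard ratios and ORR, report 95% intervals too, either alone or beside 80% intervals labelled as such.
2. Label every between-arm p-value, including those for PFS and OS, as nominal, descriptive and unadjusted for multiplicity. Make no claim of significance at 20%.
3. In SAP Section 7, record the added between-arm comparisons. If a 20% level or 80% interval is kept anywhere, record that as well, with its reason.

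The cost is SAP wording and table shells; sample size and data collection are unaffected. The price in presentation is that the main between-arm intervals become about 53% wider (1.9600/1.2816 = 1.529) than those now specified, which is the width the protocol planned.
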